## Significance

The results of this study will help determine whether by consuming a Low-carb High fat breakfast people with T2D will improve blood glucose control, increase satiety and improve body composition. This information will provide high quality scientific evidence for the potential health benefits of consuming a low-carbohydrate breakfast, as a dietary strategy for managing T2D.

## OUTCOMES MEASUREMENTS AND METHODS

The primary outcome measure is HbA1c concentrations over the 12 week period following the LCHF breakfast or the CTL breakfast. Secondary measures will include plasma glucose, insulin, blood lipid profile (triglycerides, total, HDL, and LDL cholesterol) and inflammation (high-sensitivity C-reactive protein [CRP], tumour necrosis factor [TNF]-alpha, interleukin [IL]-6). As well as hunger/satiety levels, caloric intake and body weight/ body fat mass outcomes.

### Dietary assessment

Each group will be provided with a menu and preparation instructions consisting of 8 ~400-500 kcal LCHF breakfasts (<10% carbohydrates, 65-75% fat, and 15-25% protein; e.g., omelet including low-carbohydrate additions such as cheese, meat, or non-starchy vegetables) or 8 ~400-500 kcal CTL breakfasts (45-60% carbohydrates, 20-35% fat, 15-25% protein – according to Diabetes Canada Clinical Practice Guidelines, 2018; e.g., oatmeal and berries) from which to choose each morning. Meals will be matched in calories (~400-500kcal) and protein content (15-25%). Instruction will be given for digital recording of breakfast by RedCap-UBClink. Participants will also be guided to register three 3-day food records (2 weekdays and 1 weekend day) at weeks 1, 6 and 12 of the trial using a logbook provided with instructions by the research team at initial consultation. Reminders to complete the 3-day food records will be given by telephone call, text

messages and/or emails based on participant preference. We have used this approach successfully in several recent and ongoing trials [18] [19]. Macronutrient composition and total caloric intake will be calculated using FoodWorks (The Nutrition Company) software to determine any group differences across time.

Participants will complete 100 mm Visual Analog Scales (VAS) to measure self-reported hunger, fullness and desire for sweet and savoury foods before each meal (breakfast, lunch and dinner) at weeks 1, 6 and 12. Participants will rate each of the following 4 questions by marking vertically on a horizontal line with descriptive anchors on either side (“not at all” to “extremely”): 1) How hungry do you feel; 2) How full do you feel; 3) How satisfied do you feel; 4) How much do you think you can eat? The VAS scores will be converted to a 0–100 scale, as previously described [21]. We used this approach in our supporting preliminary study [11] showing reduced pre-dinner hunger when a LCHF breakfast was consumed by people with T2D. Questionnaire is included as attachment and will be sent as link from the RedCap platform.

The Godin Leisure-Time Exercise Questionnaire allows the assessment of self-reported leisure---time physical activity. The individual is asked to complete a self-explanatory, brief four-item query of usual leisure-time exercise habits. The leisure---time physical activity score is expressed in units and can be computed in two steps. First, weekly frequencies of strenuous, moderate, and mild activities are multiplied by nine, five, and three, respectively; these three latter values correspond to MET (metabolic equivalents) value categories of the activities listed. Then, the total weekly leisure activity score is computed in arbitrary units by summing the products of the separate components. Questionnaire is included as attachments and will be sent as link from the RedCap platform.

### **Cognition test**

Questionnaire is included as attachments and will be sent as link from the RedCap platform.

### **TPB Questionnaire**

Questionnaire is included as attachments and will be sent as link from the RedCap platform.

### **Blood samples**

Blood will be collected at 2 timepoints, one at baseline and the other at the end of the trial. For the primary outcome of HbA1c, participants will be asked for results from a recent HbA1c test in 2 time points: a) less than a month from study start and b) less than one week from study end. If they a recent exam is not available, participants will be asked to go to their nearest local lab for a recent HbA1c blood test. They will receive a requisition by e-mail and will not need to pay or have a doctor’s referral for the exam. Participants with high levels of A1c (>8.5%) during screening will be notified via email and not eligible for the study. For secondary

outcomes, a dried blood spot device will be used for sampling. Dried blood spot is a form of collection where patients place blood drops on a filter card after a finger prick with a lancet. Once dry, blood spot cards are extremely stable for shipment and storage, and the dried blood format offers excellent correlation with serum tests. The same laboratory providing the blood spot will analyze primary outcome of HbA1c and associated secondary outcomes measures of fasting plasma glucose, insulin, blood lipid profile (triglycerides, total, HDL, and LDL cholesterol) and inflammation (high-sensitivity C-reactive protein [CRP]).

#### Continuous Glucose Monitoring (CGM)

A CGM device (Abbot FreeStyle Libre PRO) will be inserted into the subcutaneous adipose tissue of the participants' upper arm in order to collect continuous glucose readings during the first and last 2 weeks (14 days) of the trial. CGM sensor glucose readings are taken from the interstitial fluid (ISF), a thin layer of fluid that surrounds the cells of the tissues below the skin. The FreeStyle Libre PRO device is factory-calibrated so requires no finger stick calibrations (which reduces participant burden) and is indicated for detecting trends and tracking patterns of hyperglycemia and hypoglycemia. CGM will serve to confirm that the LCHF meal lowers the post-breakfast glucose spike and will provide details on daily postprandial hyperglycemia to be used in analyses of overall glucose control (24 h average, post-meal areas under the curve [AUC], and glycemic variability). The research team is experienced in CGM data collection and analyses having conducted >10 CGM-based studies in the last 8 years [11] [16][17] [22] [23].

[name] will be the qualified investigator overseeing the continuous glucose monitoring and to whom the CGM devices will be sold as per section 83 of the Medical Devices Regulations.

#### Height and weight

Participants will be asked to report height and weight at the beginning and end of the trial. They will be oriented to weigh themselves on the same scale both timepoints wearing minimal clothes and at same hour of the day.

#### Website

As research shifts to a remote model due to COVID-19, online resources can be extremely valuable. Utilization of a website is proposed because it can be cost effective, efficient and successful in engaging individuals for initial user feedback, recruitment, follow-up and information dissemination. The website consultation and log in will not be mandatory. Participants can use it safely as no personal information will be collected by navigation. If log in is desired, participants will receive a link to create a personal account inputting a log in and password. They will then have access to documents, recipes and news. If they do not wish to create an account, they will still receive all materials by email. The only personal information sent to research team is the email.

All this information is described on the Terms of Use and Privacy Policy links (below) in the website and on Consent Form.

Links with Private Policy and Terms of use:

<https://www.ubcbreakfaststudy.com/privacy-policy>

<https://www.ubcbreakfaststudy.com/terms-of-use>

The website was created in a Wix platform. Wix.com is a leading cloud-based development platform with millions of users worldwide. Users' and Users-of-Users' Personal Information may be stored in data centers located in the United States of America, Ireland, South Korea, Taiwan and Israel. It may use other jurisdictions as necessary for the proper delivery of Services and/or as may be required by law. More information on Privacy policy and Terms of use in link below:

<https://www.wix.com/features/main>

## Protection of Human Subjects

All participants will be given a unique study code, with all data and information gathered connected with this code. Only the PI will have access to the master list linking the codes with participant names. Participant information and data will be either stored in a locked filing cabinet, or on an internal UBC network drive accessed only through a dedicated LAN internet connection on a password protected computer in the PIs laboratory with Salto passcard access only to the members of the research lab.

REDCap will be used as project management, storage of information, sending questionnaires and processing results. The REDCap platform is a secure web application for building and managing research data collection instruments. The platform is specifically designed to support online or offline data capture for research studies. The REDCap platform runs on server infrastructure physically located in BC, Canada, at the UBC University Data Centre (UDC).

If participants perform a HbA1c test at the Laboratory, results will be transmitted by secure fax from Laboratory to UBC (fax machine located in PI's Lab which is only accessed by lab members through Salto cards).

## POTENTIAL PROBLEMS AND ALTERNATIVE STRATEGIES

Diet compliance: We will encourage accurate recording of diet by providing clear instructions and training participants on the necessary detail required. Together with the assessment of dislikes and allergies we will personalize each intervention diet and provide guidance to enhance compliance, as the recipes provided will be allow to choose from personal preference. Participants will complete a food log to record consumption of the study diets at specific timepoints (1, 6 and 12 weeks).

Since the study involves a minor modification to diet, we do not anticipate that any adverse events due to the interventions will be seen.

**Blood sampling:**

Blood collection in local labs will follow all safety protocols established by laboratory and Public Health Agency of Canada (PHAC), BC-Centre for Disease Control, and Interior Health (IH). But, there is the risk of exposure to contamination by the Coronavirus. To minimize risks, participants will receive a copy of Lab's Safety information and procedures which include social distancing and face covering measures. Blood spots: when compared to traditional wet blood and plasma collection using venipuncture, capillary blood sampling is safer and easier, so much so that nearly anyone can perform the procedure, mainly type 2 diabetes patients who are used to doing finger pricks for glucose levels. However, risks associated with the process of finger-stick blood draws are minimized by usage of sterile and disposable material as well as hygiene procedures. Participants will receive their own kit with sterile material and instructions on procedure.

**Protection of personal data:** All participants will be given a unique study code, with all data and information gathered connected with this code. Only the PI will have access to the master list linking the codes with participant names. Participant information and data will be either stored in a locked filing cabinet, or on an internal UBC network drive accessed only through a dedicated LAN internet connection on a password protected computer in the PIs laboratory with Salto passcard access only to the members of the research lab.

If participants perform a HbA1c test at the Laboratory, results will be transmitted by secure fax from Laboratory to UBC (fax machine located in PI's Lab which is only accessed by lab members through Salto cards). Exam results will be identified only by study identification number.

If participants would like to have access to their partial results, they will opt for that on the "End of Study Survey" for an "Individual End of Study Report" that will be then sent by email. It will contain participants ID and date of birth (day/month/year) plus information from their participation such as pre and post Continuous Glucose readings and HbA1c results.

REDCap will be used as project management, storage of information, sending questionnaires and processing results. The REDCap platform is a secure web application for building and managing research data collection instruments. The platform is specifically designed to support online or offline data capture for research studies. The REDCap platform runs on server infrastructure physically located in BC, Canada, at the UBC University Data Centre (UDC).

There are no risks and it is not mandatory to visit or log in to website. Most of our services do not require any form of registration, allowing participants to visit our

site without any identification. However, some services may require personal information such as name and email address. This contact information will only be used for the purposes for which it is supplied to us (e.g., responding to comments or requests for information). Once consented in the study, participants have the option to log in and access study information such as recipes, forms and communicate with Research team. This can be done by creating a log in and password using the email as the only personal information. Registering in the website is not mandatory since all documents will be provided to participants via e-mail and in a printed format.

**Informed consent and ethics:** Prior to beginning the study Informed consent will be obtained from participants and they will be informed they can withdraw at any time. For participants already enrolled in the study, the updated version will be sent by email with new information highlighted.

Participants who completed the study will be contacted via email asking if they would like an “End of Study Report”. If yes, the report will be sent by email.

## **BACKGROUND AND AIM:**

From December 2019 to June 2022, we completed the study titled “Impact of a low-carbohydrate versus low-fat breakfast on blood glucose control in type 2 diabetes” at two study sites, at the University of Wollongong (UOW) and the University of British Columbia (UBC). The aim of the trial was to determine whether a low-carbohydrate high-fat (LC) breakfast (with breakfast meals focused around eggs as a main ingredient), compared to a standard low-fat control (CTL) breakfast (designed to have no/minimal eggs) would improve blood glucose control in individuals with type 2 diabetes (T2D). The primary outcome measure was change in Hemoglobin A1C (HbA1c) following the 12-week dietary intervention. Secondary outcomes included changes in satiety and daily caloric intake, body weight, body mass index, glucose control assessed by continuous glucose monitoring, insulin, C-reactive protein, blood lipid profile, carotenoid levels, and cognitive function. It was hypothesized that consuming a LC breakfast would improve blood glucose control, increase satiety, and improve body composition and cognitive function in people with T2D.

## **SAMPLE SIZE CONSIDERATIONS**

We used a previous breakfast intervention in T2D along with our recently published one-day egg-based low-carbohydrate (LC) breakfast trial to calculate the sample size for this RCT. Rabinovitz et al  compared a “big breakfast” containing higher fat and protein providing 33% total daily energy to a small breakfast providing 12.5% daily energy over 3 months in a similar sample of participants with T2D using a similar parallel-group design. They reported an absolute reduction in HbA1c% of 0.46% in the big breakfast group. This is similar to the magnitude of change observed in a recent study by Nichols et al  who reported an average HbA1c reduction of 0.45% in response to metformin, the standard prescribed medication for people newly diagnosed with T2D. For this reason, it is reasonable to use the study published by Rabinovitz et al to estimate a clinically relevant effect size for our sample size calculation. A medium effect size (Cohen’s  $d = 0.46$ ) was calculated from the Rabinovitz study. In agreement, for our recent one-day study examining an egg-based LC breakfast (3), the effect size (Cohen’s  $d$ ) for improvements in CGM-derived glucose control variables (including AUC, iAUC, glycemic variability, and mean) ranged from  $d = 0.48-1.2$ .

Taking a conservative approach, we used an effect size of  $d = 0.4$  in the sample size calculation. The total sample size necessary to detect a between-within interaction using a repeated measures ANOVA with an effect size of  $d = 0.4$  (which corresponds to an ANOVA effect size  $f = 0.2$ ) with 90% power and 5% type 1 error with a conservative correlation among repeated measures of  $r = 0.5$  is 68 ( $n = 34$  per group, calculated using G\*Power v3.1.9.2). To account for a 20% dropout rate (2), we aimed to recruit a sample size of  $n = 41$  per group. These calculations were documented in the original grant application (Feb 2019), trial protocol (Dec 6, 2019), and SAP (Nov 17, 2021).

Adjustment as of 16th January 2022:

Recruitment was originally closed on November 2021 after  $n = 92$  participants were randomized; however, based on the nature of the remote trial and participants dropping out after randomization, only 78 participants had baseline A1c data. Unexpectedly, 4/35 participants who completed the study in one group failed to obtain follow-up A1c and 2/33 in the other group failed to obtain follow-up A1c, resulting in complete data on  $n = 31$  per group. Reasons included the impact of COVID-19 and winter holidays coinciding with study conclusion or were not reported by the participants. A blinded analysis of the primary outcome by an independent statistician not involved in any other aspect of the trial was completed on January 16, 2022. After consultation with the statistician, the research team made the decision to re-open recruitment in order to obtain sufficient sample size based on the original calculations. Using an updated estimation of loss to follow up (62 complete data out of 92 randomized = 33%), we aimed to recruit an additional 10-12 participants in order to maximize the chances of having  $n = 34$  per group for final analyses.

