#### **SENSITIVITY ANALYSIS:**

To explore robustness of the primary outcome, we will perform the following sensitivity analyses:

- We will perform sensitivity analyses on the primary outcome (change in HbA1c at 12 weeks) and secondary outcomes
  - including study site (UOW, UBC) as a covariate,
  - stratified by study site (UOW, UBC).
  - Per protocol analyses based on adherence to eating a compliant breakfast (i.e., uploaded daily breakfast photo that complies with group allocation, taking a conservative approach that if no photo is uploaded the breakfast did not comply) including only those participants who remained in the trial and had >80% adherence
  - Sub-analyses based on or controlling for breakfast egg intake

Secondary endpoints exploring within-group changes from baseline will be performed using a linear mixed model. The model will include fixed effects for timepoint (Baseline vs Week 6/12), stratified allocation factors (sex), site and random effects for participants to account for participant variability in the outcome measures.

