## HANDLING OF MISSING DATA AND OTHER DATA CONVENTIONS

No statistical imputations will replace missing data for the outcome measures (*data as observed*). However, the constrained baseline longitudinal data analysis – in a linear mixed model with restricted maximum likelihood – is a principled approach to addressing missing outcome data, including the baseline value of the continuous outcome measure. The model permits the inclusion of all participants in the analysis with either a baseline or a follow-up value. Thus, missing data will not be imputed for the ITT analyses. If a blood marker value is below the detection limit, we will explore the results following imputation of the value as limit of detection (LOD) divided by the square root of 2 (6).

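### Does the January 2022 blinded analysis, followed by re-opened recruitment, threaten the 5% error rate or call for a separate analysis of the first 92 randomised?

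*SAP*

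**What the plan says.** The SAP section Sample Size Considerations sets the target at 68 complete participants, 34 per group, "with 90% power and 5% type 1 error". Its adjustment of 16 January 2022 gives the following sequence:

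- Recruitment closed in November 2021 with 92 randomised. Of these, 62 had complete HbA1c data, 31 per group.
- "A blinded analysis of the primary outcome by an independent statistician not involved in any other aspect of the trial was completed" on 16 January 2022.
- After consulting that statistician, "the research team made the decision to re-open recruitment in order to obtain sufficient sample size based on the original calculations".
- Using the observed loss of 33%, "we aimed to recruit an additional 10-12 participants in order to maximize the chances of having" 34 per group at the final analysis.

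The section Sensitivity Analysis opens with "To explore robustness of the primary outcome, we will perform the following sensitivity analyses". It lists site as a covariate, analysis by site, a per-protocol set, and breakfast egg intake. Recruitment phase is not among them. The section Analysis Objectives, Outcomes, and Statistical Methods places the statistical analysis, blinded to allocation, after the last participant finishes.

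**The concern.** The order of events invites the question. An outcome analysis came first, and closed recruitment re-opened next. The word blinded does not settle the matter, because a comparison of coded groups still shows the size of the difference and its p-value. The stated reason needs only counts of completers, so a reader may ask what an outcome analysis was for. The January analysis also does not sit neatly with the statement that analysis follows the last participant's completion.

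The type I error is at stake. If a significant January result would have been accepted as final, the test on the enlarged sample is a second chance at the same hypothesis, and an unadjusted 5% test understates the false-positive rate. An analysis restricted to the first 92 randomised appears to offer protection, since those people were enrolled before anyone could have seen a result.

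**Working it through.** **1. The plan's own figure.** Inputs, from SAP Sample Size Considerations: f = 0.2, r = 0.5, two groups, two time points, two-sided 5%, 90% power. For the within-between interaction, λ = f² × N × 2/(1 − r) = 0.04 × N × 4 = 0.16N, referred to a non-central F with 1 and N − 2 degrees of freedom.

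| N complete | λ | Power |
|---|---|---|
| 62 | 9.92 | 87.3% |
| 66 | 10.56 | 89.3% |
| 68 | 10.88 | 90.2% |

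The target of 68 is reproduced. At 62 the trial was 6 completers, and about 3 points of power, short of its own target.

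**2. Do counts alone explain the extension?** Loss is 30/92 = 32.6%, stated as 33%. Recruits needed: 6/(62/92) = 8.9. The chance of gaining at least 6 completers, binomial with completion 62/92:

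| Recruits | P(at least 6 complete) |
|---|---|
| 8 | 0.49 |
| 9 | 0.67 |
| 10 | 0.80 |
| 12 | 0.94 |

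A range of 10-12 is what someone working from counts and wanting a good chance of reaching 68 would choose. No effect estimate enters. Expected completers are 62 + 10 × 62/92 = 68.7 to 62 + 12 × 62/92 = 70.1.

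**3. Type I error if the result had been used.** This case is an assumption; no section of either document states it. The groups are compared in January on the 62 complete cases at two-sided 5%, significance is final, and otherwise recruitment is extended and tested again at 5%. The two test statistics have correlation √(62/N), and the error is P(|Z₁| > 1.96 or |Z₂| > 1.96).

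| Final N | Correlation | Type I error |
|---|---|---|
| 68 | 0.955 | 6.4% |
| 70 | 0.941 | 6.6% |
| 72 | 0.928 | 6.7% |
| 74 | 0.915 | 6.9% |

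The last two rows require every recruit to supply data, against an observed loss of 33%. If recruitment were extended only after a January p-value between 0.05 and 0.10, the error would be 6.0-6.1%. If the extension did not depend on the result, it is 5.0%.

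**4. What an analysis of the first 92 could show.** Take the 62 complete cases as the information in that set. The chance that the full test is significant and the first-92 test is not:

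| True effect | N = 68 | N = 70 |
|---|---|---|
| None | 1.4% | 1.6% |
| λ = 0.16N (the plan's inputs) | 3.7% | 4.5% |
| λ = 0.04N | 6.1% | 7.3% |

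The third row is included because λ = Nd²/4 for a difference in change scores. The plan's 0.16N therefore corresponds to d = √0.64 = 0.8, while d = 0.4 on the change gives 0.04N.

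Under no effect, the 1.4-1.6% is the same whether or not the January result was used: a trial that is non-significant in January is extended under either account. Observing the discordance therefore does not discriminate between the two accounts.

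**The case for a change.** The strongest opposing case is that both omissions are real and cheap to fill. The SAP is silent on the content and recipients of the January output. A few sentences and one extra model run would let readers judge for themselves, and the first-92 test keeps its nominal level whatever prompted the extension. Participants with a single HbA1c value could contribute, since "The model permits the inclusion of all participants in the analysis with either a baseline or a follow-up value".

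The silence stands: the SAP contains no explicit assurance that the result was set aside. The extra analysis, however, delivers less than it promises.

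- Under the feared rule, recruitment is extended only when January is non-significant. If the January analysis used the same people and model, the first-92 test is then non-significant by construction and adds nothing to the January result.
- A significant first-92 result would count against the feared rule. A non-significant one is expected in 95% of trials with no effect, so it settles nothing.
- The guarantee of level assumes that the model was fixed before January. The current SAP text post-dates that analysis and uses a constrained model with sex, whereas the protocol's Statistical Analysis section names a mixed model with age and sex. The November 2021 SAP is not among the documents. The guarantee therefore also rests on someone's account.
- Such an analysis, added after the January look, would not be prespecified in any useful sense.

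The timing statement in the SAP reads most naturally as referring to the final analysis. The January analysis is openly dated and described in the same document, so nothing is hidden by the apparent mismatch.

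**Conclusion.** No change to the plan follows. The SAP discloses the date of the January analysis, its blinding, the independence of the statistician, the completer counts and the reason for re-opening. The arithmetic bears that reason out: about 9 recruits were needed and 10-12 were sought. On the documented reason the 5% level holds. The extension restored power from 87.3% to about 90% at the plan's inputs.

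Inflation to 6.4-6.6%, or at most 6.9% if no recruit is lost, requires three things that the documents do not state: groups were compared in January, a significant result would have ended the trial, and anything else led to extension. These figures also assume that the January analysis used the 62 complete cases, a set that the SAP does not specify.

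The remaining gap is one of narrative detail. What was computed and who saw it would ordinarily be described when the trial is reported, together with any January comparison of the groups if one was made. An analysis of the first 92 is a reasonable optional extra, but it would alter neither the primary analysis nor its error rate, and it could not establish why recruitment was re-opened.
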